### 6.3.9 Rescue Therapy: Series of Definitions

Rescue will be defined from narrow to broad, based on the type, timing, intensity, and reason for treatment. These treatments may be considered rescue therapy for anemia secondary to chronic kidney disease: ESA medication, and RBC transfusion.

The possible reasons for such treatments include:

- Investigator-ordered rescue (per protocol for worsening of anemia),
- Adverse events (unrelated to anemia),
- Maintenance during prolonged interruption of study treatment, and
- Inadvertent use (at hospital or dialysis center).

If a given therapy starts the same day as permanent discontinuation of study drug, then that therapy will be considered on treatment for rescue definitions.

For the vadadustat arm, any use of ESA may be considered rescue. For the control arm, the study drug itself is an ESA and so is not necessarily rescue, yet change to another ESA may be considered rescue. Because darbepoetin alfa is titratable, increase in dose is not considered rescue unless the investigator specifically designates it as such; however, increases in dose relative to last dose will be characterized in three categories by percentage increase: <50%,

Statistical Analysis Plan AKB-6548-CI-0014 and AKB-6548-CI-0015

$\geq 50\%$  and  $< 100\%$ , and  $\geq 100\%$ . Subjects will be presented by their maximum category of increase within each of the four analysis time periods in Year 1 (see [Section 5.1](#)). All ESA use will be converted to IV epoetin alfa equivalents.

The CRFs collect reasons for ESA medication and RBC transfusion. The series of rescue definitions are defined as follows:

- Narrow: Rescue for worsening anemia with ESA medication or RBC transfusion defined in [Section 6.3.7](#) and [Section 6.3.8](#), not starting after permanent study treatment discontinuation.
- Broad-on-treatment: Any exposure to ESA medication (aside from darbepoetin alfa not designated as rescue in the control arm) or RBC transfusion for any reason not starting after permanent study treatment discontinuation.

In addition to the sensitivity analyses ([Section 9.1.4](#)), the report will include a summary of the incidence, timing, duration, intensity, and frequency for each definition of rescue, including a Kaplan-Meier plot of time to first rescue.

## 7 NON-MACE SAFETY ENDPOINTS

While the primary safety endpoints relate to MACE, defined as all-cause mortality, nonfatal myocardial infarction, or nonfatal stroke, this SAP addresses only the non-MACE endpoints. As stated above, a separate SAP will describe the analyses of MACE and the individual components of the MACE endpoint as well as expanded MACE definitions where expanded MACE will include hospitalization for heart failure and thromboembolic events.

The safety reporting period for this study begins upon randomization and ends at the final protocol-required study contact. A treatment-emergent adverse event (TEAE) is one that begins or worsens after treatment initiation. The AE CRF has been designed to capture all events after randomization. AEs that occur during the screening period are not reported on the CRF. The treatment groups will be compared with respect to the following non-MACE safety endpoints:

- Adverse events (AEs) and serious adverse events (SAEs)
- Treatment-emergent adverse events (TEAEs) and treatment-emergent SAEs
- Vital signs and clinical laboratory values (see [Appendix E](#))
- Adverse events of special interest (AESI) (see [Appendix F](#))
- Any value of Hb  $> 12.0$  g/dL;  $> 13.0$  g/dL,  $> 14.0$  g/dL,  $< 9.0$  g/dl or  $< 8.0$  g/dl
- An Hb increase  $> 1.0$  g/dL within any 2-week interval or  $> 2.0$  g/dL within any 4-week interval.

## 8 PHARMACOKINETIC/PHARMACODYNAMIC (PK/PD) ANALYSIS

Serum samples will be taken and stored for use in biomarker studies. PK sample will be collected between 15 minutes to 1 hour after vadadustat administration at baseline visit, and will also be performed along with other study laboratory samples being collected at the Weeks 4, 12, 28, and 52. For each visit, one serum sample is collected for each subject. Descriptive analysis of PK concentration will be provided by treatment groups. Analysis for EPO is listed in [Section E.1.7](#)

## 9 EFFICACY ENDPOINTS AND ANALYSES

This section briefly describes the methods to be used for each of the efficacy endpoints. Rather than providing details for each endpoint, the accompanying Appendices describe the approaches to be used for specific types of data. For all the models and methods described below, see [Appendix B](#) for handling of any missing data.

The general approach to analysis of continuous outcomes will be analysis of covariance (ANCOVA) with multiple imputation for missing data or mixed models for repeated measurements (MMRM) on observed data. For a description of the models to be used, see [Appendix C](#).

For binary variables, the general approach will be Mantel-Haenszel estimation of risk difference stratified ([Mantel, 1954](#)) by the baseline strata with (or without) multiple imputation to deal with missing data. See [Appendix D](#).

Some endpoints come from count data (e.g., the number of RBC transfusions) that are likely to have a spike at zero and a long tail. Such data are often complicated to analyze because of their highly skewed distributions. While the samples sizes are so large that the Central Limit Theorem ensures that the means of these distributions are essentially normal, some interpretation of the nature of the distributions may be useful clinically. To the extent reasonable, we have described the planned methods for such data, but ad hoc methods may be necessary if the skewness is extreme. See [Appendix D](#) for the general approach.

For time-to-event variables, the general approach will be to use Cox models stratified by the baseline randomization strata. See [Appendix D](#).

### 9.1 Definition of Primary Efficacy Endpoint: Change from Baseline in Hb

The primary efficacy endpoint is the change in average Hb between baseline and the PEP (Weeks 24 to 36).

The primary analysis will use the randomized population. As described in [Section 2.7](#), establishment of noninferiority will be based on a margin of -0.75 g/dL applied to the difference in mean change: vadadustat minus darbepoetin alfa.

#### 9.1.1 Baseline Hb

Baseline Hb will be calculated as the average of the last 2 central laboratory Hb measurements of samples taken at the visits prior to or on the date of first dose date.

Subjects may be rescreened up to three times. A minimum of 1 Hb value is required for the calculation of baseline.

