8.4.4 Dosing and Dose Adjustment Guidelines

Dosing will be initiated at the Baseline visit, and the first dose of study medication (vadadustat or darbepoetin alfa) will be administered at the investigative site after other Baseline visit procedures have been completed. The investigator may elect to postpone the initial dose of study medication until a subsequent visit based on the subject's Hb level or Hb trajectory assessed at the Baseline visit, or based on timing of last ESA dose given during Screening.

For all subjects, it is recommended that no additional ESA doses be administered after SV2 and prior to the Randomization visit.

Year 1-4 Treatment Period Visits

Hemoglobin will be monitored via HemoCue throughout the study to determine if the dose of study medication (vadadustat or darbepoetin alfa) will be adjusted, interrupted, or maintained. From Weeks 0 to 12, Hb will be obtained via HemoCue every 2 weeks for monitoring for dose adjustment. From Week 12 to Week 52, Hb will be monitored every 4 weeks via HemoCue.

From Week 53 through the study end, Hb will continue to be monitored via HemoCue to determine if the dose of study medication will be adjusted, interrupted, or maintained. Any unscheduled measurement taken between study visits will be recorded in the appropriate CRF and the subject's source when a Hemocue is taken. Hemoglobin will also be assessed with a CBC through the central laboratory for efficacy and safety evaluations; however, dose adjustments should be based on the HemoCue Hb value. If the Investigator has an immediate clinical concern about a subject's HemoCue value, the Investigator may use clinical judgment and repeat the HemoCue Hb, use local lab values, or wait for central lab results. The test method utilized to inform your treatment decision must be recorded in the appropriate CRF and subject's source.

Year 2-4 Monthly Hb Monitoring

Additionally, after Week 52, the Hb drawn as part of the local standard of care labs must be monitored monthly for dosing oversight. Per the Dosing Algorithms, if the Hb value suggests a dose adjustment is needed, an unscheduled visit must be performed.

If monthly standard of care labs are not available, a study unscheduled visit must be performed. This visit will include, at minimum, the Hb measurement via HemoCue, dose adjustment assessment, and adverse events assessment.

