8.4.4.1 Vadadustat Dosing and Dose Adjustment Algorithms

Subjects assigned to vadadustat will initiate dosing at 2 tablets once daily (300 mg/day). Dose levels of vadadustat utilized in this study include 150, 300, 450, and 600 mg (available tablet strength is 150 mg).

Dosing will be initiated at the Baseline visit and the first dose of vadadustat will be administered at the investigative site (study physician's clinic) after other Baseline visit procedures have been completed. The Investigator may elect to postpone the initial dose of study medication until a subsequent visit based on the subject's Hb level or Hb trajectory assessed at the Baseline visit, or based on timing of the last ESA dose given during screening.

Thereafter, vadadustat will be taken once daily on an outpatient basis. Subjects may take vadadustat with or without food and should be instructed to swallow the tablet(s) whole. Subjects should be instructed to take vadadustat at roughly the same time each day.

During the study, vadadustat should be dosed according to the Dose Adjustment Algorithm in [Appendix C: Vadadustat Dosing and Dose Adjustment Algorithms](#).

For subjects progressed to DD-CKD, and continuing on vadadustat, the dose adjustment should be based on the Dose Adjustment Algorithms (Appendix C: Vadadustat Dosing and Dose Adjustment Algorithms).

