11 DATA ANALYSIS

Data collected throughout the study will be summarized using descriptive statistics and listed in by-subject listings. Continuous variables will be summarized using number of subjects with

data, mean, standard deviation, median, minimum, and maximum. For categorical variables, the number and percentage of subjects in each category will be tabulated. Summaries will be provided by treatment group within appropriate analysis populations (as defined in [Section 11.2, Study Analysis Populations](#)) and by time point/time period as appropriate.

For Hb, Baseline will be calculated as the average of the central laboratory Hb measurements of samples taken at the screening visit closest to the date of randomization and the measurement taken at randomization. For other parameters, unless otherwise specified, Baseline will be defined as the last available value prior to the first dose of study medication.

Hemoglobin values as assessed through the central laboratory will be used for efficacy and safety evaluations; local HemoCue Hb values will be used only for dose adjustments.

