## 1 INTRODUCTION

This statistical analysis plan (SAP) covers the two PRO2TECT studies, Protocols AKB-6548-CI-0014 and AKB-6548-CI-0015, hereafter referred to as CI-0014 and CI-0015, respectively.

The SAP supports the Statistical Methods Section of the clinical study reports (CSRs). It elaborates upon the protocol-specified endpoint definitions and the formal statistical methods that will be used in analyzing both studies. Unless otherwise specified, all analyses will be conducted for each study separately.

Throughout this SAP, planned analyses of both studies are identical to each other except in those places that specifically identify where the plans diverge. Akebia does not intend to pool data together for formal efficacy and general safety analyses; however, analyses of major adverse cardiovascular events (MACE) will be pooled from both studies. A separate SAP will describe the planned methodology for the MACE analyses.

If the analyses described in the protocols differ from those in this SAP, the methods of the SAP prevail.

This SAP contains language and programming code that specifies the exact intent of each analysis. The sponsor will finalize and sign this document prior to locking the database and unblinding (see [Section 2.5](#)). Many of the analyses described in this SAP are quite complex. A blinded team of clinicians and statisticians will review the data carefully to develop conventions and analytic methods not anticipated in writing this SAP.

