## 5.2 Definition of Baseline

In general, the baseline value will also be the value of assessment closest to the end of the window, i.e., Day 1 (first dose date). The baseline value must be assessed prior to initiation of study treatment. In contrast, the baseline value for laboratory-based efficacy outcomes (e.g., Hb, ferritin, hepcidin, TSAT, serum iron, TIBC, and lipids) will be an average of the last 1 or 2 values prior to or on the first dose date, as specified in [Section 9.1.1](#).

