### C.1. Analyses using ANCOVA

#### C.1.1. Primary Analysis

The primary analysis is based on the change in average Hb between the baseline and the primary efficacy period (PEP), Weeks 24 to 36. The noninferiority analysis will be based on a margin of -0.75 g/dL applied to the mean change in vadadustat minus darbepoetin alfa. To establish noninferiority, the lower limit of the confidence interval of the mean change in vadadustat minus darbepoetin alfa must be -0.75 g/dL or higher. If the lower limit of the 2-sided 95% confidence interval for the difference between the mean in the vadadustat group and the mean in the darbepoetin alfa group is above zero, superiority will have been established and the finding will be interpreted as providing evidence of a greater change from baseline in Hb for vadadustat relative to the control arm.

The primary efficacy analysis is based on the estimated confidence interval estimated from an ANCOVA model. The computation of this confidence interval is described in this section. Modifications for additional continuous endpoints are outlined in a separate section.

The ANCOVA model will be fit using PROC GENMOD in SAS with the following variables:

- HB\_BL – this is the average of the last 2 Hb measure on or prior to the first dose date
- DELT\_HB3 – this is computed as the average Hb measure computed from the PEP (Week 24 to 36) visits minus HB\_BL
- TRT – denotes treatment group; vadadustat or darbepoetin alfa
- STRAT1 – stratification factor of geographic region (US, EU, versus Rest of World)
- STRAT2 – NYHA CHF class 0 or I versus II or III

The basic SAS code to fit the model is in [Exhibit C 1](#), but the full process includes multiple imputed datasets as seen in [Exhibit B 2](#).

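### SAP baseline Hb is tied to the first dose rather than randomization, so for subjects whose first dose is postponed it can contain post-randomization values

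*SAP*

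**What the plan says.** Three places in the SAP define baseline Hb by the first dose date. Section 9.1.1 reads "Baseline Hb will be calculated as the average of the last 2 central laboratory Hb measurements". At least one value is required, and the values that qualify come from "samples taken at the visits prior to or on the date of first dose date". Section 5.2 says that the baseline for laboratory-based efficacy outcomes "will be an average of the last 1 or 2 values prior to or on the first dose date". Section C.1.1 describes the model covariate HB_BL: "this is the average of the last 2 Hb measure on or prior to the first dose date".

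Section 11 of the current protocol (Amendment 7-COL) anchors the same quantity to randomization. It averages the central-laboratory "samples taken at the screening visit closest to the date of randomization and the measurement taken at randomization". SAP Section 1 settles which text governs: "If the analyses described in the protocols differ from those in this SAP, the methods of the SAP prevail".

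The two dates can separate. Randomization takes place at the Baseline visit (protocol 6.1) and treatment is open label (8.4.3). Under protocol 8.4.4, "The investigator may elect to postpone the initial dose of study medication until a subsequent visit", on the basis of Hb level or trajectory at the Baseline visit or the timing of the last ESA dose in screening. Sections 8.4.4.1 and 8.4.4.2 repeat this for each arm. Central blood counts are scheduled at Baseline and at Weeks 2, 4, 6 and onward (9.3.4, 9.3.5).

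**The concern.** Baseline Hb enters the primary analysis twice: it is subtracted to form the change score (SAP 9.1.3) and it is the ANCOVA covariate (9.1.4, C.1.1). It also feeds the imputation model (Table B 1), the MMRM (C.2) and the secondary endpoint (C.1.3). SAP 9.1.4 presents the primary analysis as a comparison by assignment in the randomized population.

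A covariate measured after open-label allocation can be influenced by that allocation. If investigators postpone more often in one arm, and Hb drifts in the meantime, the arms' baselines differ for a reason that randomization did not create. The adjustment then carries that difference into the treatment estimate. The entry-Hb stratum, the other Hb variable fixed before randomization, is left out of the model (9.1.4). No sensitivity analysis in 9.1.5 uses a baseline anchored to randomization.

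**Working it through.** **1. The plan's own figure.** Inputs from protocol 11.1.1 and SAP 2.7: margin -0.75 g/dL, SD 1.5, true difference 0, 925 per arm, two-sided 95% interval.

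- SE = 1.5 × √(2/925) = 0.070; half-width = 1.96 × 0.070 = 0.137 g/dL.
- Power: 0.75/0.0697 - 1.96 = 8.8 standard errors, so above 99.9%. The stated figure of more than 90% is confirmed.
- For 90% power: 2 × 1.5² × (1.960 + 1.282)² / 0.75² = 84.1, so 85 per arm.

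Changing the baseline anchor changes none of these.

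**2. Which values enter.** This assumes that the visit schedule keeps running from the Baseline visit and that no other central blood count intervenes.

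| First dose at | SAP: last two values | Protocol Section 11 | Weight w of post-randomization values |
|---|---|---|---|
| Baseline visit | last screening, Baseline | last screening, Baseline | 0 |
| Week 2 | Baseline, Week 2 | last screening, Baseline | 0.5 |
| Week 4 | Week 2, Week 4 | last screening, Baseline | 1 |

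**3. Size of the bias.** Let Δp be the arm difference in the share postponed (vadadustat minus darbepoetin), d the Hb drift in the post-randomization values, and b the slope of follow-up Hb on baseline. The arm difference in mean baseline is D = Δp × w × d. The raw change score is biased by -D. In the ANCOVA the subtracted baseline is also the covariate, so the bias is -b × D. The documents give none of Δp, d or b; all values below are assumptions.

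- Low case: 5 points, individual baseline shift (w × d) of 0.25 g/dL, b = 0.3: 0.05 × 0.25 = 0.0125; × 0.3 = 0.004 g/dL.
- High case: 20 points, shift of 0.5 g/dL, b = 0.3: 0.20 × 0.5 = 0.10; × 0.3 = 0.03 g/dL.
- Widest range tried (absolute values): 5 to 30 points, drift of 0.3 to 1.0 g/dL, w of 0.5 or 1. Raw bias runs from 0.05 × 0.5 × 0.3 = 0.0075 to 0.30 × 1 × 1.0 = 0.30. In the ANCOVA it runs from 0.0075 × 0.3 = 0.002 to 0.30 × 0.5 = 0.15 g/dL.

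**4. Simulation check.** True difference 0, 925 per arm, 1,500 replicates. The subjects postponed are those with the highest Hb at randomization. Drift is -0.5 g/dL per two weeks, except in the equal-share row (-0.3).

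| Postponed, vadadustat / darbepoetin | Post-randomization values | Mean ANCOVA difference, first-dose anchor |
|---|---|---|
| 10% / 10% | one of two | -0.0002 |
| 20% / 5% | one of two | 0.014 |
| 20% / 5% | both | 0.049 |
| 5% / 20% | both | -0.049 |
| 30% / 0% | both | 0.097 |

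With the randomization anchor the mean stayed within 0.0013 of zero in every scenario. The sign follows the arm that is postponed more: if Hb falls during the delay, more postponement on vadadustat favours vadadustat.

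**5. Against the decision rules.** A shift of 0.03 is 0.03/0.75 = 4% of the margin and 0.03/0.070 = 0.43 SE. With a true difference near zero, the lower limit is expected near -0.137, far from -0.75. For the superiority reading (SAP 9.1.4), a shift of 0.43 SE in vadadustat's favour at a true difference of zero raises the one-sided error from 2.5% to P(Z > 1.96 - 0.43) = P(Z > 1.53), about 6.3%.

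**The case against.** The case against has real substance.

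- **The protocol is not uniform.** Only Section 11 names randomization. Sections 5.2, 11.1.1 and 11.6.1 speak of mean Hb before treatment, and 11.5 averages the qualifying values in the period before treatment. A first-dose anchor is a fair reading of those passages. This stands: it is a mismatch to be reconciled, not a clear departure from a single protocol rule.
- **Few subjects may be affected.** Dosing at the Baseline visit is the default. The definitions differ only for someone postponed past another central blood count; HemoCue readings do not count, and unscheduled visits require no central sample (9.3.11). This stands.
- **Unequal postponement is not shown.** The rule and its triggers are the same in both arms and rest on information available by the Baseline visit. With equal postponement the simulated bias is about zero. This also stands: open-label allocation makes unequal use possible, no more.
- **Undosed subjects are covered.** Footnote b to SAP Table 1 uses the randomization date when there is no first dose. It does not help subjects dosed late.
- **Study days and windows also run from the first dose** (SAP 5, 5.1). Moving the baseline alone gives postponed subjects two time origins. This is true, but the change score remains well defined, and the windows are a separate question.

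A reader might infer that the definition breaks the randomized comparison or contradicts the treatment-policy estimand. The documents do not support that. The estimand in SAP 9.1.4 concerns keeping subjects who are never treated, stop, are rescued or withdraw, and all of them stay in. Bias arises only if postponement, or the drift that follows it, differs by arm.

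**Conclusion.** The point holds as a correctable inconsistency in the primary endpoint. The governing SAP text lets post-randomization Hb values into the baseline and the covariate for subjects whose first dose is postponed past a further central blood count. Section 11 of the protocol would not. The resulting bias is conditional on postponement differing by arm, and its direction cannot be known in advance.

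Under the assumed rates and a slope of 0.3 the effect is about 0.004 to 0.03 g/dL. About 0.10 in the simulation, or 0.15 by formula, needs a 30-point imbalance with both baseline values post-randomization; the 0.15 also needs a 1.0 g/dL drift and a slope of 0.5. That last figure just exceeds the 0.137 half-width. Noninferiority at -0.75 is unlikely to change unless the lower limit lies very close to the margin. The superiority reading against zero is more exposed. The sample size and the power statement are unaffected. Whether dosing may be postponed is a clinical matter and is not judged here.

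**What to change.** In SAP 5.2, 9.1.1 and C.1.1, define baseline Hb as the average of the last two central-laboratory values on or before randomization: the last screening value and the randomization value. Keep the minimum of one value and apply the rule to all randomized subjects, dosed or not. This agrees with protocol Section 11. Carry the same variable through Table B 1, C.1.3 and C.2. The first-dose-anchored baseline may be kept as a sensitivity analysis, and the number of postponed first doses should be reported by arm. The SAP also covers CI-0014, so the wording should be checked against that protocol too.

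The cost is a short edit in three places. The central blood count is already drawn at the Baseline visit (protocol 9.3.4), so no new data are needed. For subjects dosed at that visit the two definitions normally give the same value.
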